Our **hypotheses** are the following:

Hypothesis 1: ACTH gel is superior to no treatment in maintaining remission in children with frequently relapsing or steroid dependent nephrotic syndrome.

Hypothesis 2: Relapses in children with frequently relapsing or steroid dependent nephrotic syndrome receiving ACTH gel will increase when the dose of ACTH gel is reduced by 50%.

Hypothesis 3: ACTH gel will increase the percentage of children with frequently relapsing or steroid dependent nephrotic syndrome that remain relapse free off medication.

Primary end-points:

The primary end-point related to Hypothesis 1 is the proportion of patients in each arm with a relapse during the initial 6 months of treatment.

The primary end-point related to Hypothesis 2 is the proportion of relapse-free patients during the first 6 months and second 6 months of treatment with ACTH. This will include patients initially randomized to ACTH and patients who receive ACTH as rescue therapy following their initial relapse in patients randomized to no treatment.

The primary end-point related to Hypothesis 3 is the proportion of patients who have relapses in the 6 months following completion of one year of ACTH. This will be compared to the

proportion of patients with relapses during the initial 6 months in the patients randomized to no treatment.

Secondary end-points:

Our secondary end-points are the following:

1. The total prednisone exposure over the initial 12 months in the two groups.
2. The number of relapses over the initial 6 months in the two groups.
3. The change in BMI, height SDS, and cholesterol over the study period for both groups

Study Design and Methods

The experimental design is a multi-center, prospective, controlled open label, randomized trial comparing ACTH gel and no treatment in preventing relapses in pediatric patients with frequently relapsing or steroid dependent nephrotic syndrome.

Patients will be randomized in a 1:1 ratio to either no treatment or treatment with ACTH gel. The primary outcome will be the presence of a relapse within 6 months of starting ACTH gel or no treatment.

After initial recruitment, enrollment will begin with a screening visit to determine eligibility and obtain informed consent and assent. Randomization and weaning of all other medications for the treatment of NS will begin after remission has been achieved for those with active relapse. There will be a 2 week overlap of ACTH and current immunosuppressive medications:

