1. ACTH will be initiated 2 weeks prior to the completion of the prednisone taper for patients who are receiving prednisone at the time of consent.
2. ACTH will be initiated 2 weeks prior to stopping preventive medications such as tacrolimus, cyclosporin, and mycophenolate.

Patients randomized to no treatment will be followed for up to 6 months or until disease relapse, whichever occurs first. Patients who relapse within 6 months will be given the option of reassignment to the ACTH treatment group after remission has been achieved using conventional corticosteroid therapy.

Patients randomized to ACTH treatment will be given ACTH for 12 months. During the second 6 months, the ACTH dose will be reduced to 50% of the starting dose. The outcome of interest is the presence of relapses after dose reduction. Follow-up will occur throughout the 12 months of therapy, and also for 6 months following the completion of ACTH therapy. The outcome of interest is the percentage of patients with relapses in the 6 months after completing a 12 month course of ACTH treatment.

Visits

Screening visit: The study will be explained to the patient and family. Inclusion and exclusion criteria will be reviewed to determine eligibility. Consent and assent will be obtained as appropriate. Medical history will be recorded. A physical exam will be performed. If indicated, a

plan for prednisone tapering will be explained to the family. The date of the baseline visit will either be determined at that visit or via telephone for patients who are currently in relapse.

Baseline visit: The patient will be seen and have baseline labs (renal function panel, cholesterol, urinalysis, urine protein/creatinine ratio). A urine pregnancy test will be performed in females of childbearing age (achieved menarche) who are randomized to ACTH treatment along with counseling in required birth control. An interval medical history and quality of life (QOL) survey will be performed. Patients will have a physical examination. Patients will be randomized to either ACTH gel or no treatment. Patients will be given Albutix and instructions for daily monitoring of the urine and recording the results. Patients randomized to ACTH gel will receive their first injection in clinic and be taught how to perform injections at home. A stop date for other immunosuppressive medications will be provided, if appropriate, 2 weeks after starting ACTH.

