ACTH Treatment ACTH will be dosed by body surface area (BSA), with an initial dose of 80U per 1.73m². After 6 months of treatment, the initial dose will be reduced by 50% (1st reduction), to complete the second 6 months of ACTH therapy.

If patients develop significant side effects on the initial dose, they will have an early dose reduction by 50% at the discretion of each individual site PI (1st reduction). They will complete a total 6 months of treatment with the initial and reduced dose. After 6 months, ACTH will be reduced again by 50% (2nd reduction), to complete the second 6 months of ACTH therapy.

Patients who do not tolerate ACTH therapy despite an early dose reduction will exit the study with reporting of adverse events as appropriate.

Patients who relapse on a reduced dose of ACTH during the second 6 months of treatment will have their dose reverted to the previous dose and complete a total of 12 months of treatment with no further dose reductions.

Patients with two relapses on the highest tolerated ACTH dose will exit the study.

| BSA | Initial Dose | 1st Reduction (50%) | 2nd Reduction (25%) |
|------------|---------------------|----------------------------|----------------------------|
| 0.50-0.60 | 24U = 0.3mL | 12U = 0.15mL | 8U = 0.1mL |
| 0.61-0.75 | 32U = 0.4mL | 16U = 0.2mL | 8U = 0.1mL |
| 0.76-0.95 | 40U = 0.5mL | 20U = 0.25mL | 12U = 0.15mL |
| 0.96-1.09 | 48U = 0.6mL | 24U = 0.3mL | 12U = 0.15mL |
| 1.10-1.25 | 56U = 0.7mL | 28U = 0.35mL | 16U = 0.2mL |
| 1.26-1.45 | 64U = 0.8mL | 32U = 0.4mL | 16U = 0.2mL |
| 1.46-1.60 | 72U = 0.9mL | 36U = 0.45mL | 20U = 0.25mL |
| ≥ 1.61 | 80U = 1.0mL | 40U = 0.5mL | 20U = 0.25mL |

*Note: there is rounding of the doses to the closest administrable amount by subcutaneous injection.

Interval Visits

Telephone contact will occur weekly for the first 3 weeks after randomization. This will include screening for adverse events, reviewing medications and timing of medication changes, review of Albustix testing, and reviewing dosing of ACTH if applicable. Patients randomized to ACTH treatment will have two additional telephone contacts one month after ACTH dose reduction or discontinuation. This is to screen for symptoms of adrenal insufficiency.

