Follow-up visits in patients randomized to ACTH will occur 1 month, 2 months, 4 months, 6 months, 8 months, 10 months, 12 months, 15 months and 18 months after the baseline visit. An interval medical history (including screening for adverse events) will be performed. Patients will have a physical examination. A renal function panel, cholesterol, urinalysis, urine protein/creatinine ratio, and QOL survey will be obtained at months 6 and 12. Urine pregnancy test, if applicable, will be obtained at months 4 and 8.

[figure not shown]
The dose of ACTH will be reduced by 50% after 6 months of treatment. Patients who have significant side effects attributed to ACTH will have an earlier dose reduction (i.e., before 6 months) at the discretion of each individual site PI. The PI will be asked to review possible side effects with the patient at each visit and decide if a dose reduction is warranted. A telephone contact will be made 1 month after dose reduction to screen for symptoms of adrenal insufficiency.

Relapses will be treated with prednisone, at 2mg/kg/day or 60mg/m²/day (maximum dose 60 mg) until remission is achieved, with a subsequent taper off therapy over 4 weeks. For patients receiving a reduced dose of ACTH, the dose will be reverted back to the last effective dosage on which remission was sustained, and continue at that dose until the end of the study. If >1 relapse occurs on the initial ACTH dose, ACTH therapy will be considered a failure and terminated.

The total ACTH therapy duration will be 12 months, after which, the subjects will be seen at follow-up at 15 and 18 months.

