Patients who are randomized to no treatment will have follow-up visits up to the time of relapse, at 1 month, 2 months, 4 months, and 6 months. An interval medical history (including screening for adverse events) will be performed. Patients will have a physical examination. A renal function panel, cholesterol, urinalysis, and urine protein/creatinine ratio, and QOL survey will be obtained at month 6. They will be treated with prednisone for any relapses and have the option to be placed on ACTH during the last 2 weeks of the prednisone taper if the relapse occurred within 6 months of the baseline visit. The subsequent visit schedule and procedures will be identical to the schedule for subjects initially randomized to ACTH (i.e., it will include a baseline visit, telephone contacts, and 18 months of follow-up). Alternatively, the patient may elect to be treated via standard of care in collaboration with the treating nephrologist, and the patient will then exit the study.

Flow Chart of Study Course

Participant Selection

Sixty subjects will be recruited from 10-12 large pediatric centers. Subjects may also be identified via physician or self-referral from advertisements placed on NephCure. Additionally, subjects may be recruited from registries of individuals interested in research participation.

Patients and their caregivers will be approached during a relapse of nephrotic syndrome or within 4 months of a relapse. The following criteria will be reviewed during the screening visit to determine eligibility:

Inclusion criteria

1. Age >1 year at onset of nephrotic syndrome
2. Age 2-20 years at time of randomization
3. Estimated GFR > 50 ml/min/1.73 m² at most recent measure prior to randomization (Schwartz formula)
4. Steroid responsive nephrotic syndrome throughout clinical course (never required a second agent to attain remission of a relapse of nephrotic syndrome)
5. History of frequently relapsing or steroid dependent nephrotic syndrome (defined as 2 or more relapses within 6 months after initial therapy or 4 or more relapses in any 12 month period OR relapse during taper or within 2 weeks of discontinuing prednisone).
6. Patient is currently in relapse of nephrotic syndrome or had a relapse within the last 4 months (defined as an increase in the first morning urine protein to creatinine ratio ≥ 2 or Albustix reading of ≥ 2 for 3 or 5 consecutive days).

Exclusion criteria

1. Prior treatment with ACTH.

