Using the method of Lan-DeMets, we list the boundary p-value for this sequential design. Thus, after our first interim look, we will reject the null hypothesis of equal 6 month relapse rates between ACTH gel and no treatment if our test statistic renders a p-value $< .006$. According to the intent to treat principle, patients will be analyzed according to the treatment they have been assigned to during the randomization procedure. The odds ratio of ACTH versus no ACTH, plus the Wald 95% confidence interval, will be also be calculated.

The primary end-point related to specific aim 2 is the proportion of relapse-free patients during the first 6 months and second 6 months of treatment with ACTH. This will include patients initially randomized to ACTH and patients who receive ACTH as rescue therapy following their initial relapse. We will estimate 6 month and 12 month relapse-free rate using the method of Kaplan-Meier and compare treatments using a log-rank test.

The primary end-point related to specific aim 3 is the proportion of patients who have relapses in the 6 months following completion of one year of ACTH. This will be compared to the proportion of patients with relapses during the initial 6 months in the patients randomized to no treatment using a z test statistic. Odds ratios of ACTH vs no ACTH will also be calculated.

We will also compare patients as randomized by secondary endpoints such as total prednisone exposure in 12 months, number of relapses, cholesterol and change in BMI with two sample t-tests. If normality assumptions do not hold, appropriate non-parametric methods will be used.

Growth data collected during the study will be summarized descriptively for each treatment group at each time point. Based on height data collected during the study and published reference height information, the height standard deviation score (SDS, also called z-score) will be computed for each patient at each time point as:

$$(\text{Height} - \text{mean height for that age category}) / \text{SD of height for that age category}.$$

Descriptive statistics of this endpoint will be presented by time point and the z-scores will allow identification of potential outliers.

Treatment Assignment and Randomization

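### The Hypothesis 2 log-rank test names no groups; the comparison its end-point implies is within-child, which an ordinary log-rank test and a cumulative 12-month Kaplan-Meier rate do not serve

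*Combined protocol and SAP*

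**What the plan says.** Under Hypotheses and End-points, the Hypothesis 2 end-point is "the proportion of relapse-free patients during the first 6 months and second 6 months of treatment with ACTH". The set is children randomised to ACTH plus children from the no-treatment arm who take ACTH after a relapse. The Statistical Analysis section repeats this for specific aim 2 and then gives the whole method in one sentence: "We will estimate 6 month and 12 month relapse-free rate using the method of Kaplan-Meier and compare treatments using a log-rank test". It does not say which groups are compared or how two periods from one child are handled.

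The dose schedule is common to the set:

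- Randomised children (Study Design and Methods): "During the second 6 months, the ACTH dose will be reduced to 50% of the starting dose".
- Rescued children (Interval Visits): "The subsequent visit schedule and procedures will be identical to the schedule for subjects initially randomized to ACTH". Rescue is optional: "Alternatively, the patient may elect to be treated via standard of care".
- Children reduced early for side effects (ACTH Treatment): "After 6 months, ACTH will be reduced again by 50% (2nd reduction), to complete the second 6 months of ACTH therapy".

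Some children will have no months 6-12 outcome on ACTH. ACTH Treatment states "Patients with two relapses on the highest tolerated ACTH dose will exit the study" and also has children leave if they cannot tolerate ACTH after an early reduction. Interval Visits states "If >1 relapse occurs on the initial ACTH dose, ACTH therapy will be considered a failure and terminated".

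**The concern.** A log-rank test needs two groups, and this set offers no parallel pair that differs in scheduled dose reduction. Hypothesis 2 is one of three hypotheses given its own primary end-point, yet the analyst would have to choose the contrast, possibly after seeing data. Two of the three obvious choices do not test the hypothesis. The third does, but it uses the same children twice, and the named test assumes independent groups. The planned 12-month rate also does not estimate the second half of the stated end-point.

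**Working it through.** **1. Candidate contrasts.**

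| Reading of the sentence | Does it test halving? |
|---|---|
| Randomised versus rescued ACTH | No. Both are scheduled for reduction at month 6, and rescued children were selected by having relapsed. |
| ACTH versus no treatment | No. It is outside the aim 2 set and repeats Hypothesis 1; the no-treatment arm is followed for at most 6 months. |
| First versus second 6 months on ACTH | Yes, subject to confounding with time, but the same children form both groups. |

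**2. Inputs.** The plan gives no Hypothesis 2 figure to reproduce. From the Statistical Analysis section: 30 per arm, and 6-month relapse of 30% on ACTH and 70% on no treatment. Assumed: N = 30 if no control switches, or 30 + 0.70 × 30 = 51 if every expected control relapser does; constant hazard within each period; hazard doubled after halving; gamma frailty with mean 1 and variance v from 0 to 2; two-sided 5%.

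**3. The 12-month Kaplan-Meier rate.** With no dose effect and no differences between children, the relapse-free proportion is 0.70 in each period, but the cumulative 12-month rate is 0.70 × 0.70 = 0.49. With frailty, S(x) = (1 + vx)^(−1/v), and H is set so that S(H) = 0.70. At v = 1, H = 1/0.70 − 1 = 0.429 and S(2H) = 1/1.857 = 0.538. At v = 2, S(2H) = 0.570. So the 12-month rate is 49-57% when the end-point's value is 70%.

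Restricting period 2 to children relapse-free at month 6 does not repair this. With no dose effect, their period-2 risk is 1 − 0.538/0.70 = 23% at v = 1 and 1 − 0.570/0.70 = 19% at v = 2. That biases against the hypothesis.

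**4. Period log-rank versus paired test, complete pairs.** With the hazard doubled, the discordant probabilities are b = S(H) − S(3H) (relapse in period 2 only) and c = S(2H) − S(3H) (period 1 only). Approximate McNemar power is Φ{[(b − c)√N − 1.96√(b + c)] / √[(b + c) − (b − c)²]}.

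At v = 1, S(3H) = 1/2.286 = 0.4375, so b = 0.2625 and c = 0.101. With N = 51, power = Φ[(1.153 − 1.182)/0.581] = 48%. The simulated figures below are ranges over repeated runs.

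| v | b | c | McNemar, formula | Mid-p McNemar, simulated | Period log-rank, simulated | Log-rank type I error |
|---|---|---|---|---|---|---|
| 0 | 0.357 | 0.147 | 56% | 55-56% | 59-60% | 5.1% |
| 0.25 | 0.327 | 0.132 | 54% | 54% | 54% | 4.2% |
| 0.5 | 0.302 | 0.120 | 52% | 52% | 49-50% | 3.8% |
| 1 | 0.263 | 0.101 | 48% | 48-49% | 39-40% | 2.5% |
| 2 | 0.207 | 0.077 | 41% | 41% | 24-25% | 1.2% |

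With N = 30, log-rank versus mid-p McNemar power is 39 v 36%, 35 v 35%, 30 v 32%, 23 v 29% and 12 v 23% in the same order.

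**5. A different model.** With lognormal frailty, 30% versus an assumed 50% relapse, N = 51 and within-child correlation of about 0, 0.24, 0.46 and 0.56, McNemar power is 55, 66, 83 and 90%. Log-rank power is 56, 57, 63 and 62%. The direction agrees; the absolute power does not.

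**6. Randomised versus rescued ACTH.** A 12-month log-rank test at v = 0, 0.5, 1, 2 rejects in 5, 9, 13, 19% of trials with no dose effect and in 5, 10, 15, 23% with a doubled hazard. It hardly responds to dose.

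**7. Incomplete pairs.** Children removed for repeated relapse all relapsed in months 0-6, so excluding them lowers the period-1 risk of those left. At v = 0 with no time off risk after a relapse, 5.0% are removed and the remaining period-1 risk is (0.300 − 0.050)/(1 − 0.050) = 26%, against 30% in period 2 with no dose effect. Mid-p type I error at N = 51 is then about 6.5-7.5%. It is 5.3-5.7% if 1.4 months per relapse are off risk (assumed from prednisone to remission plus the 4-week taper).

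Counting these children as relapsed in months 6-12 makes them concordant, so the McNemar p-value is the same as under exclusion. Counting them as not relapsed makes them discordant against the hypothesis: at v = 1, N = 51, power is 15-22% instead of 55-61%. The equal-p result does not extend to a child who leaves for intolerance without a relapse in months 0-6.

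**The case against.** The sentence can be read sensibly. The end-point points to first versus second 6 months, which does address dose, and on that reading the log-rank test equals or slightly beats McNemar when children hardly differ. The documents give no frailty value, so the gain from pairing is assumed. This stands, and it limits the size of the point. It does not supply the missing groups or make the 12-month rate a second-period proportion.

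A paired test also needs a rule for incomplete pairs, whereas Kaplan-Meier can censor, and excluding repeat relapsers can push its type I error above 5%. That stands too, and the fix must meet it.

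Three stronger readings are tempting but unsupported:

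- That ignoring the pairing inflates false positives. With complete pairs it does the opposite. Only with exits, and at the extreme of the range (v = 2, no off-risk time, N = 51), did log-rank type I error come near 7%.
- That power for Hypothesis 2 is low by any method. No power was calculated in the plan, and step 5 reaches 83-90% under other assumptions.
- That every child is certain to be reduced at month 6. ACTH Treatment schedules a second reduction after an early one. Interval Visits says a child who relapses on a reduced dose returns to the last effective dose and stays on it to the end of the study, without limiting this to months 6-12. The two sections conflict for a child reduced early who relapses before month 6.

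**Conclusion.** The point holds as a defect in the stated analysis of Hypothesis 2: the contrast is unnamed, the implied contrast is paired and the named test is not, and the 12-month Kaplan-Meier rate is not the second-period proportion. The first and last of these follow from the text and simple arithmetic. The power cost is conditional: nil at frailty variance 0 to 0.25, about 9 points at 1 and 17 at 2 with 51 complete pairs and a doubled hazard. It should be fixed, but its reach is limited. The plan bases its power on the randomised 6-month comparison, which is unaffected. No analysis removes the confounding of dose with time on treatment, since every child goes from the higher to the lower dose in the same order.

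**What to change.** In the specific aim 2 paragraph of Statistical Analysis, replace the log-rank sentence with the following:

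- **Contrast and test.** A within-child comparison of any relapse in months 0-6 versus months 6-12 of ACTH, keeping children who relapsed in months 0-6. Use mid-p McNemar and report the paired difference in proportions with its 95% confidence interval. A mixed or GEE logistic model with period as covariate is an acceptable alternative; choose one in advance.
- **Incomplete pairs.** One main rule, for example complete pairs, with bounds counting each child without a months 6-12 outcome as relapsed and as not relapsed. Name all three routes: ACTH terminated after more than one relapse on the initial dose, exit after two relapses on the highest tolerated dose, and exit for intolerance. Note that excluding repeat relapsers can raise type I error as in step 7.
- **Kaplan-Meier.** By period, with the clock restarted at month 6, as description only.
- **Limits.** State that dose is confounded with time on treatment and that no power was calculated for Hypothesis 2.

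Separately, reconcile ACTH Treatment and Interval Visits on whether a child reduced early who relapses before month 6 has a further reduction at month 6, and then say how the analysis classifies such children.

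The analysis change is wording only. The end-point, visits and sample size stay, and it uses relapse and dose data the trial needs anyway. The cost is up to about 4 points of power against the log-rank test (59.3% v 55.5%, N = 51) if children do not differ in relapse tendency.

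### Aim 3 compares children who complete a year of ACTH with all randomised controls in an earlier window, so its z test cannot by itself support Hypothesis 3

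*Combined protocol and SAP*

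**What the plan says.** Hypothesis 3 has its own primary end-point and states that "ACTH gel will increase the percentage of children with frequently relapsing or steroid dependent nephrotic syndrome that remain relapse free off medication" (Hypotheses and End-points). The Statistical Analysis section tests it by setting "the proportion of patients who have relapses in the 6 months following completion of one year of ACTH" against the share of "patients with relapses during the initial 6 months in the patients randomized to no treatment using a z test statistic", and adds odds ratios. No sample size or power is given for aim 3.

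The ACTH group is not named in aim 3. Aim 2, by contrast, expressly includes both children randomised to ACTH and children who receive it as rescue. In Study Design and Methods, a paragraph about children randomised to ACTH says: "The outcome of interest is the percentage of patients with relapses in the 6 months after completing a 12 month course of ACTH treatment".

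Three rules can end ACTH before one year. Under ACTH Treatment: "Patients who do not tolerate ACTH therapy despite an early dose reduction will exit the study" and "Patients with two relapses on the highest tolerated ACTH dose will exit the study". Under Interval Visits: "If >1 relapse occurs on the initial ACTH dose, ACTH therapy will be considered a failure and terminated".

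For controls, "Patients randomized to no treatment will be followed for up to 6 months or until disease relapse, whichever occurs first" (Study Design and Methods). Under Interval Visits, a control who relapses within 6 months may start ACTH on the same 18-month schedule, or leave for standard care. The intent-to-treat sentence in Statistical Analysis follows the aim 1 test.

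**The concern.** The ACTH proportion is conditional on finishing a year of treatment; the control proportion is conditional on nothing after randomisation. One of the reasons for not finishing is repeated relapse, so the children removed are likely to be those with the highest underlying risk. The control exit cannot do the same, because it comes after the event has been counted.

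Analysis by assigned arm does not repair this. A child who never completes a year has no post-completion window, so assignment alone supplies no outcome.

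The windows also differ in calendar and disease time. Inclusion criterion 6 requires a current relapse or one within 4 months, so control risk is measured soon after a relapse. ACTH risk is measured in months 12-18, when no untreated child is under follow-up.

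At stake is the claim of lasting benefit. It could come from who is left in the ACTH group, or from a change in untreated risk over a year, rather than from ACTH.

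**Working it through.** **Inputs from Statistical Analysis.** 30 children per arm; 6-month relapse 70% untreated and 30% on ACTH; two-sided z test at 0.05; 91% power for aim 1 with boundary p-values 0.006 and 0.045.

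**The plan's own figure.** With unpooled variance the standard error is √[(0.7×0.3 + 0.3×0.7)/30] = √0.014 = 0.118, and 0.40/0.118 = 3.38. The boundary 0.045 is z = 2.005, so the final look alone gives Φ(3.38 − 2.005) ≈ 91.6%. Adding the first look gives 91.7%, which agrees with 91%. This concerns aim 1 only.

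**Selection by simple arithmetic.** Suppose ACTH has no lasting effect, so off-drug relapse is 70% across the whole arm. Let e be the share that does not complete and q their off-drug relapse risk (both assumed). Then

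completer rate = (0.70 − e×q)/(1 − e).

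- e = 10%: q = 85% gives (0.70 − 0.085)/0.90 = 68.3%; q = 100% gives 66.7%. Exact one-sided false benefit with 27 completers is 4.0% and 5.3%.
- e = 20%: q = 85% gives (0.70 − 0.17)/0.80 = 66.2%; q = 100% gives 62.5%. With 24 completers, 5.6% and 9.5%.
- q = 70%: the rate stays at 70%. The test's discreteness then gives 2.4-3.0%, depending on the number of completers.

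**Selection with the exit rule modelled.** Assumed: Poisson relapses with gamma frailty of variance v between children; rates calibrated to 70% and 30% by λ = [(1 − p)^(−v) − 1]/v, or −ln(1 − p) when v = 0; 10% intolerance unrelated to risk; exit at two relapses on the initial dose; the same relapse rate on the reduced dose; no lasting effect. With 20,000 trials per setting, the simulation error near 5% is about √(0.05×0.95/20,000) = 0.15 points.

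| Variance | Completers of 30 | Their relapse rate | One-sided false benefit (nominal 2.5%) |
|---|---|---|---|
| 0 | 25.2 | 70.0% | 2.6% |
| 0.5 | 24.3 | 67.8% | 3.8% |
| 1 | 23.6 | 66.3% | 5.0% |
| 2 | 22.5 | 64.2% | 7.1% |

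Sensitivity, for variance 0.5-2 unless stated:

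- An 8-week gap without relapse after each relapse lowers the last column to 3.6-4.8%.
- Reduced-dose relapse of 50%, in the direction Hypothesis 2 predicts, raises it to 4.1-8.1%.
- On-drug relapse of 50% gives 8-13% at variance 0.5-1 and 22% at variance 2.
- With intolerance set to 0%, variance 0.5 and 1 give 3.7% and 5.0%. Intolerance as modelled thins the group without selecting on risk.

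**If switched controls were counted on the ACTH side** (planned rates, variance 0.5/1/2). If all relapsed controls switch, the ACTH-side rate is 70.8/71.4/72.2% and false benefit 1.7/1.5/1.3%, so the bias turns slightly against ACTH. If half switch, false benefit is 2.8/2.3/2.6%, close to nominal. In either case the same children would sit in both groups of a test that assumes independent samples.

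**Keeping all 30 in the denominator.** At variance 1, 23.6 × 0.663 = 15.6 completers relapse and 6.4 children do not complete. Counting non-completers as relapse-free gives 15.6/30 = 52%; counting them as relapsed gives 22.0/30 = 73%. The width of that range is simply the share not completing.

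**Non-concurrence.** The documents give no untreated relapse rate for months 12-18, so no size can be calculated.

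**The case against.** The strongest reply has four parts.

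*The ACTH group is clear enough.* The paragraph in Study Design and Methods concerns children randomised to ACTH, and aim 2 adds rescue patients where aim 3 does not. The ordinary reading is the randomised arm. This largely stands: one sentence would settle it. But it is also the reading under which selection can favour ACTH, and it brings no rule for non-completers.

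*The effect is small and rests on outside assumptions.* This stands. Frailty variance and intolerance are not in the documents, and without frailty there is no bias.

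*The windows are not so different.* Both open around withdrawal of active treatment, and in the model about 38-43% of completers (variance 0.5-1) relapse during the ACTH year. This softens the contrast but does not supply an untreated comparison in months 12-18.

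*Counting every non-completer as relapsed would be worse.* As a replacement primary analysis, yes. It treats intolerance as relapse, gives 73-75% against 70% when there is no lasting effect, and can show false harm: 4-6% at planned rates, 13-18% (variance 0.5-1) if ACTH does not work on drug.

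Stronger conclusions are tempting. A reader might infer that aim 3 has a grossly inflated error rate. Rates of 17-33% do arise if on-drug relapse is 70% (variance 0.5-1), but Hypothesis 1 would then succeed in only about 2.5% of trials, and both claims together in 1.5-2.1%. The plan states no rule that makes aim 3 depend on aim 1, so the case is possible, but it is not the planned one. Likewise, an assumed fall in untreated relapse to 60% gives 16-20% (variance 0.5-1), but nothing in the documents supports that figure. A reader might also infer that the bias always favours ACTH, which the switched-control results contradict.

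**Conclusion.** The concern holds in a limited form. Aim 3 as written is a comparison of a selected group with a randomised one, in different periods, presented as the test of a hypothesis with its own primary end-point.

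At the planned 70% and 30%, with no lasting effect and the assumed frailty and intolerance, selection lowers the ACTH-side relapse rate by 0-6 points and raises one-sided false benefit from 2.5% to at most about 7%. It grows if the drug works less well than planned. Non-concurrence is a separate limit: its size is unknown, and no choice of denominator removes it. The documents do not support calling the aim 3 result invalid or its bias large. They do support saying that a significant z test would not by itself establish lasting benefit. Hypothesis 1 and its 91% power stand.

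**What to change.** In the SAP:

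1. State that the aim 3 ACTH group is the children randomised to ACTH. Report switched controls separately, as description.
2. Report the number, timing and reasons of non-completion.
3. Keep the completer proportion, but label its comparison with controls as non-randomised and non-concurrent. State that its z test and odds ratio cannot alone support Hypothesis 3.
4. Add a sensitivity analysis with all children randomised to ACTH in the denominator. Show the range from all non-completers counted as relapsed to all counted as relapse-free, and use observed relapse status where follow-up exists.

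The version that counts all non-completers as relapsed should stay a sensitivity analysis. At a true off-drug relapse of 40% its power is about 35-40%, against about 66% if off-drug status were known for all 30; at 30% it is about 61-63% against 90%.

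The sections on early ending of ACTH must also be reconciled. ACTH Treatment has children leave the study after two relapses on the highest tolerated dose. Interval Visits only terminates ACTH, refers to the initial dose, and schedules visits at 15 and 18 months for those randomised to ACTH. Whether follow-up continues after termination decides how much of item 4 can use observed data.

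The cost is SAP wording and a little analysis, plus a weaker claim for Hypothesis 3.
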